3.9.1 Visit 1: Pre-Operative Screening

Once informed consent has been obtained, the subject will be assigned a screening number and the following pre-operative assessments will be performed at the Pre-Operative Screening visit

- 1. Assess Inclusion/Exclusion criteria
- 2. Obtain relevant vital signs (height / weight)
- 3. Identify relevant medical history
- 4. Demographics
- 5. Assess for Neuroma
- 6. Pain Assessments (VAS, PROMIS®) prior to nerve block
- 7. Pain Assessment (VAS) post nerve block (if applicable)
- 8. Quality of Life Questionnaires (FHSQ
- 9. Concomitant Medication review and Daily Pain Medication Diary issuance (treatments including quantity and class of pain medications, dispense and review with subject)
- 10. Dispense Daily Pain Diary (review instructions with subject)
- 11. For subjects with multiple neuromas, additional Neuroma Information must be captured for each neuroma treated.

3.9.2 Visit 2: Operative Day, Day 0

The following will be collected during the Operative Day:

- 1. Verify Inclusion/Exclusion criteria
- 2. Obtain Vital signs
- 3. Document Operative Information: description of nerve injury presentation and location, and implantation information see sequence below¹⁹
- 4. Randomization (comparative study only)
- 5. Pain Assessments (VAS, PROMIS®) prior to nerve block, if not performed during screening
- 6. Pain Assessment (VAS) post nerve block, if not performed during screening
- 8. Concomitant Medication review and Daily Pain Medication Diary review (treatments including quantity, quality and class of pain medications, review with subject and re-educate if needed)
- 9. Daily Pain Dairy (review with subject prior to Pain Assessments, re-educate if needed)
- 10. Adverse Events review

The following sequence of steps will take place intraoperatively for the Nerve Cap group: 19

- 1. After debridement and mobilization of the nerve stump, determine the nerve diameter in millimeters (mm).
- 2. Select an Axoguard® Nerve Cap to fit the nerve stump, accounting for post-operative swelling and to allow easy insertion of the nerve stump into the device. If there is no Axoguard® Nerve Cap that matches the diameter of the nerve stump, select the device that is one size larger.
- 3. Hemostasis of the proximal nerve stump must be achieved prior to beginning the entubulation procedure. If a tourniquet is used, release the tourniquet and achieve hemostasis before entubulating.
- 4. Open the outer carton and remove the chevron pouch. Using standard aseptic technique, open the pouch and pass the inner tray into the sterile field for further handling.
- 5. Open the tray and fill the pre-molded reservoir with room temperature sterile saline or sterile Lactated Ringer's solution. Allow the Axoguard® Nerve Cap to hydrate for at least 10 seconds or until the desired handling characteristics are achieved, but not more than 20 minutes. NOTE: Small diameter Axoguard® Nerve Caps may need to be hydrated by flushing the lumen of the cap with solution. Care should be taken to avoid puncturing the Axoguard® Nerve Cap during this process.
- 6. Transfer the Axoguard® Nerve Cap from the reservoir and entubulate approximately 3-5 mm of the nerve stump into the Nerve Cap. Entubulate the stump by passing the suture (non-absorbable) through the wall of the tube from outside to inside at least 2 mm from the edge. Then pass the suture transversely through the epineurium of the nerve stump at a distance of at least 1 mm from the cut nerve face. Reverse the suture and pass it through the wall of the Axoguard® Nerve Cap by pulling the suture so that the nerve stump is drawn into the cap. Ensure that the nerve stump face is linearly aligned within the cap. To reduce the potential risk for misalignment, avoid abutting the nerve stump up to or inserting past the internal partition.
- 7. Tie suture securely being careful not to generate excess tension at the suture site. If desired, add sutures to secure the device to the nerve stump.
- 8. The lumen of the Axoguard® Nerve Cap may be gently filled/flushed with sterile saline or Lactated Ringer's solution. Ensure the nerve stump is not expelled from the tube while irrigating the lumen.
- 9. Once the Axoguard® Nerve Cap is securely sutured onto the nerve stump, the distal tab of the Nerve Cap may be sutured to a plane of surrounding soft tissue if desired (e.g., muscle or fascia). Tie the suture so that it is secure but avoid generating tension on the nerve when securing.
- 10. Prior to surgical site closure, visually confirm final alignment of the nerve within the cap.
- 11. Close the surgical site as required by your institutional practices or professional judgement concerning patient care.
- 12. Discard any unused portions of the Axoguard® Nerve Cap according to institutional guidelines for biological waste.

3.9.3 Visit 3: Post Operative Visit, Day 14/Week 2

Visit 3 (Week 2) is a safety visit and the following will be performed.

- 1. Obtain relevant vital signs (height / weight)
- 2. Post-Operative Care
- 3. Wound Assessment (safety check remove sutures, wound check, etc.)
- 4. Pain Assessments (VAS, PROMIS®)
- 5. Concomitant Medication review and Daily Pain Medication Diary review (treatments including quantity and class of pain medications, review with subject and re-educate if needed, dispense new diary)
- 6. Daily Pain Diary (review with subject, re-educate if needed, dispense new diary)
- 7. Adverse events review

3.9.4 Visits 4: Months 1

The following will be performed at Visits 4:

- 1. Obtain relevant vital signs (height / weight)
- 2. Wound Assessment
- 3. Pain Assessments (VAS, PROMIS®)
- 4. Quality of Life Questionnaires (FHSQ
- Concomitant Medication review and Daily Pain Medication Diary review (treatments
 including quantity and class of pain medications, review with subject and re-educate if
 needed, dispense new diary)
- 7. Daily Pain Diary (review with subject, re-educate if needed)
- 8. Adverse Events review

3.9.5 Visits 5-7: Months 3, 6, 9

The following will be performed at Visits 5 through 7:

- 1. Obtain relevant vital signs (height / weight)
- 2. Pain Assessments (VAS, PROMIS®)
- 3. Quality of Life Questionnaires (FHSQ
- Concomitant Medication review and Daily Pain Medication Diary review (treatments
 including quantity and class of pain medications, review with subject and re-educate if
 needed, dispense new diary)
- 6. Daily Pain Diary (review with subject, re-educate if needed)
- 7. Adverse Events review

3.9.6 Visit 8: End of Study/Early Termination Visit, Month 12

The following will be performed at Visit 8/End of Study/Early Termination:

- 1. Obtain relevant vital signs (height / weight)
- 2. Wound Assessment
- 3. Pain Assessments (VAS, PROMIS®)
- Quality of Life Questionnaires (FHSQ
- 6. Concomitant Medication review and Daily Pain Medication Diary review (treatments including quantity and class of pain medications, review with subject)
- 7. Daily Pain Diary (review with subject)
- 8. Adverse Events review

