Number of Subjects per Treatment Group: Enroll approximately 15 evaluable subjects in the pilot study. Enroll approximately 86 additional subjects for the randomized comparative study.

Duration of Study: Up to 13 months including screening period.

Inclusion Criteria:

Potential Subjects must:

- 1. Be able and willing to provide documented informed consent prior to the conduct of any study procedures;
- 2. Be an adult male or non-pregnant female ≥ 18 years of age;
- 3. Report baseline pain scores of >65mm on a 100mm Visual Analog Scale (VAS) at screening;
- 4. Have a documented diagnosis of symptomatic neuroma of at least one interdigital nerve in the foot which cannot be repaired to a distal nerve end;
- 5. Must have the of the following:
 - Pain with at least 3 of the following characteristics: burning, sharp, shooting, electric, parasthesias, numbness, cold intolerance;
 - Symptoms in a defined neural anatomic distribution
 - History of nerve injury or suspected nerve injury Must have at least 1:
 - Positive response to local anesthetic injection
 - US or MRI confirmation of neuroma
- 6. Be candidates indicated for surgery to address a symptomatic neuroma;
- 7. Have sufficient healthy soft tissue available to adequately cover the Axoguard® Nerve Cap;

- 8. In the surgeon's opinion, be likely to achieve complete resection of the symptomatic neuroma and be able to undergo implantation with the Axoguard[®] Nerve Cap or complete the neurotomy procedure in the control group;
- 9. Be willing and able to comply with all aspects of the treatment and evaluation schedule over a 12-month duration.

Exclusion Criteria:

Potential subjects must not:

- 1. Have undergone surgical treatment of pain from symptomatic neuroma in the target nerve(s)on three or more occasions;
- 2. Have biomechanical pathology and associated pain (such as plantar fasciitis, bursitis, sesamoid bone pain, tendinitis, etc);
- 3. Have a life expectancy of less than 12 months;
- 4. Have a history of or planned radiotherapy in the area of the end-neuroma;
- 5. be contraindicated for soft tissue implants.; this includes but is not limited to any pathology that would limit the blood supply; compromise healing or indicate the presence of a local infection;
- 6. Have a history of chronic ischemic conditions of the extremity;
- 7. Have a diagnosis of type 1 Diabetes Mellitus; or uncontrolled Type 2 Diabetes Mellitus (at the discretion of the investigator);

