1. INTRODUCTION

1.1 Background

A neuroma is formed when a peripheral nerve's continuity is substantially disrupted or injured. Nerve trauma types include cut nerves as in amputations or autograft sites, crushed nerves in carpal tunnel syndrome, or stretched nerves from high velocity accidents. When a disrupted nerve cannot be repaired, Schwann cells, attempting to restore axonal continuity, proliferate ahead of the injury site. This process creates a path through which axons grow in a disorganized fashion. In severe tissue damage the regenerating axons cannot reach their target tissue, and instead form a tangled bulbous mass which causes pain when stimulated.^{2,3}

There is no currently accepted technique that has been clinically shown to prevent or mitigate neuroma formation. With more than 700,000 peripheral nerve injuries that require surgery every year and a rapidly increasing number of diabetes-related limb amputations, the number of patients suffering from debilitating neuroma pain is significant and increasing.⁴ Painful neuroma following amputation is a disabling condition for which treatments are not usually satisfactory.⁵

Currently available treatment options after limb amputation or an unrepaired transected nerve injury incompletely address pain-inducing neuroma formation.⁶ Treatments include both surgical methods to remove neuromas or limit neuroma pain with pharmacological therapies directed at pain management. Attempts to treat symptomatic neuroma formation have been met with limited success, which is reflected by the recorded use of over 150 physical and chemical treatment methods, none of which have been uniformly successful.^{7,8,9}

VAS pain scores have consistently been the measure of choice for assessing treatment interventions for pain, but the minimum clinically significant difference has typically been reported as a reduction between 14-20 mm. ^{11, 12}

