3.4.2 Inclusion Criteria

To be considered for enrollment, subjects must meet the following inclusion criteria:

Table 3.4.2-1: Inclusion Criteria

Potential Subjects must:

- 1. Be able and willing to provide documented informed consent prior to the conduct of any study procedures;
- 2. Be an adult male or non-pregnant female \geq 18 years of age;
- 3. Report baseline pain scores of \geq 65mm on a 100mm Visual Analog Scale (VAS) at screening;
- 4. Have a documented diagnosis of symptomatic neuroma of at least one interdigital nerve in the foot which cannot be repaired to a distal nerve end;
- 5. Must have the following:
 - Pain with at least 3 of the following characteristics: burning, sharp, shooting, electric, parasthesias, numbness, cold intolerance;
 - Symptoms in a defined neural anatomic distribution
 - History of nerve injury or suspected nerve injury

Must have at least 1:

- Positive response to local anesthetic injection
- US or MRI confirmation of neuroma
- 6. Be candidates indicated for surgery to address a symptomatic neuroma;
- 7. Have sufficient healthy soft tissue available to adequately cover the Axoguard® Nerve Cap;
- 8. In the surgeon's opinion, be likely to achieve complete resection of the symptomatic neuroma and be able to undergo implantation with the Axoguard[®] Nerve Cap or complete the neurotomy procedure in the control group;
- 9. Be willing and able to comply with all aspects of the treatment and evaluation schedule over a 12-month duration.

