3.5.2 Efficacy Endpoints

Primary Efficacy Endpoints

- 1. The change in VAS score at 3 months compared to baseline (pilot phase)
- 2. The change in VAS score at 12 months compared to baseline (comparative phase)

Secondary Efficacy Endpoints

- 1. The change in VAS score at 1, 3, 6, 9 and 12 months compared to baseline
- 2. The change in PROMIS® score at 1, 3, 6, 9 and 12 months compared to baseline
- 3. The change in FHSQ score at 1, 3, 6, 9 and 12 months compared to baseline
- 4. Changes in pain medication use at 1, 3, 6, 9 and 12 months compared to baseline
- 5. Rate of recurrence of symptomatic neuroma within 12 months

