3.6 Assessments, Questionnaires, Surveys, Diaries

3.6.1 Pain Assessments - VAS and PROMIS®

Pain Assessments (VAS and PROMIS®) will be completed by the subject at the screening visit and all six (6) follow-up visits after the Daily Pain Diary review. Pain assessments may also be done on the operative day (but prior to nerve block or surgical intervention) if the nerve block is planned to occur at this time.

The Visual Analog Scale (VAS) is a pain scale designed in such a way that it allows a study subject to rate their pain with minimum constraints.³⁴ Subjects will rate their current pain level by creating a mark on a 10 centimeter (100 millimeter) line. The distance measured from 0 millimeter to the patient's mark corresponds to the amount of pain the subject is currently experiencing. The open line gives the subject the greatest freedom to choose their pain's exact intensity. VAS data are recorded as the number of millimeters from the left of the line with the range 0-100, with 0 millimeter representing no pain, and 100 millimeters representing the most pain.

PROMIS[®] is a set of person-centered measures that evaluate and monitor physical, mental, and social health in adults and children. Measures are applicable to the general population and to those with

chronic conditions. For this study, PROMIS® measures will be used to monitor a subject's physical health/pain.

Quality of Life Questionnaires (FHSQ) Quality of Life Questionnaires (FHSQ) will be completed by the subject at visits 1, 4, 5, 6, 7, and 8.

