Wound Assessment			x	X				X
Pain Assessments ³	X	X	X	X	X	x	X	X
Quality of Life Questionnaires ⁴	X			Х	X	х	х	X
Daily Pain Medication Diary and Concomitant Medication Log ⁵	х	Х	х	х	Х	Х	х	х
Daily Pain Diary	X	X	X	X	X	X	X	X
Adverse Events		X	х	x	X	X	x	X
	nstances. Visit 1 and							

^{*}Note: In some instances, Visit 1 and Visit 2 can occur on the same day.

Vital signs to include weight, seated systolic/diastolic BP measured in millimeters of mercury (mm Hg), HR (beats per minute), respiration rate (breaths Vital signs to include weight, seated systolic/diastolic BP measured in millimeters of mercury (mm Hg), HR (beats per minute), respiration rate (breaths per minute), and temperature in degrees Celsius (°C). Obtain at the beginning of each visit before any additional assessments are completed. Height will only be recorded one time at visit 1

2 Comparative study only

3 Pain Assessments: VAS and PROMIS® (for V2 Operative Day 0, VAS and PROMIS® performed prior to nerve block, nerve block oNLY if nerve block is performed during screening visit).

4 Quality of Life Questionnaires include: FHSQ

Beile Provided the Provided Provide

^{5.} Daily Pain Medication Diary (including quantity, quality and class of pain medications) related to the nerve injury should be collected during Screening and Operative day and any changes/additions should be collected during the study.

6. Definitions and Terminology

Baseline

Baseline may be considered to be Day 0 (day of the procedure) or the screening period prior to Day 0 depending on appropriateness for the analysis.

Baseline Value

For purposes of analysis, the baseline value is defined as the value captured at the baseline assessment. If this value is not available, the most recent value obtained prior to the repair will be used for the baseline value.

Change from Baseline

Change from baseline will be calculated as post-baseline value – baseline value, unless otherwise noted.

Study Day

Study Day is defined relative to Day 0: Study Day = event date - date of Day 0.

Days on Study

Days on Study is the number of days from Day 0 to the date of study completion or early termination.

Completed Subjects

The treatment period is defined as the time period during which subjects are expected to be evaluated post implantation up to 12 months. Subjects who are evaluated at the last scheduled visit determined by the investigator at each site for each patient will be defined as study completers.

Lost to Follow-Up

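### The only pre-block pre-operative VAS the visit procedures guarantee is the screening mark that had to reach 65 mm, and the SAP leaves baseline open, so the pilot and within-arm VAS changes may include regression to the mean

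*Protocol*

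**What the plan says.** **Entry.** The synopsis criterion reads "Report baseline pain scores of >65mm on a 100mm Visual Analog Scale (VAS) at screening". Section 3.4.2 sets the same cut as 65 mm or more. Both call the qualifying score the baseline score and place it at screening.

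**When the VAS is taken before surgery.**
- Section 3.9.1 item 6 (screening) lists, without condition, "Pain Assessments (VAS, PROMIS®) prior to nerve block".
- Section 3.9.2 item 5 (Day 0) lists "Pain Assessments (VAS, PROMIS®) prior to nerve block, if not performed during screening".
- Section 3.6.1 requires the VAS at screening and at the six follow-up visits. For Day 0 it says only "Pain assessments may also be done on the operative day (but prior to nerve block or surgical intervention"), and only where the block is planned for that time.
- Appendix B and the SAP schedule put an X for pain assessments at Visit 2. Footnote 3 restricts this to cases where a block is done at screening. It is unclear whether that restriction covers the pre-block mark or only the post-block one.

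**Which mark is the baseline.** SAP section 6: "Baseline may be considered to be Day 0 (day of the procedure) or the screening period prior to Day 0", according to what suits the analysis. If the baseline value is missing, the latest value before the repair is used. Visits 1 and 2 may fall on the same day.

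**Where it is used.** The pilot primary endpoint is "The change in VAS score at 3 months compared to baseline (pilot phase"), in a single arm, and SAP 9.1.2 summarises it descriptively. The comparative primary endpoint is the randomised difference in change at 12 months. Protocol 5.5.1 also calls for a 95% confidence interval on the Nerve Cap group's mean VAS change, to test a null hypothesis H0B whose wording is not visible in the public text.

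**The concern.** No subject can meet criterion 3 without a screening VAS, so the condition in 3.9.2 item 5 is not triggered for the VAS. Under the procedural sections, the default baseline is the mark on which the subject was selected for being high. A score selected that way falls on average at the next measurement even if nothing has changed, and a change-from-baseline endpoint counts that fall as relief.

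The pilot has no control arm, so its mean change cannot separate this fall from an effect of the device. The same applies to each arm's own VAS change in the comparative phase and to the single-arm interval in 5.5.1. The SAP does not settle the matter: it allows either occasion, and its fallback does not exclude a VAS taken after a nerve block, which would be a pre-repair value but not a usual pain level.

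**Working it through.** **The plan's own figure.** There is none to reproduce. The documents give no screening distribution, SD or test-retest correlation for the VAS. The values below are assumptions. Only the 65 mm cut and the 14-20 mm yardstick (Protocol 1.1: "the minimum clinically significant difference has typically been reported as a reduction between 14-20 mm") come from the protocol.

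**Formula.** Let the VAS among candidates be normal with mean m and SD s, the same on both occasions, with correlation r between screening and follow-up and no true change. For subjects selected at 65 mm or more, with a = (65 − m)/s, the expected fall is

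(1 − r) × s × φ(a) / (1 − Φ(a)).

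**Screening mark as baseline, r = 0.7:**

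| m | s | a | φ(a)/(1 − Φ(a)) | Expected fall (mm) |
|---|---|---|---|---|
| 60 | 15 | 0.333 | 1.021 | 0.3 × 15 × 1.021 = 4.6 |
| 60 | 20 | 0.250 | 0.964 | 0.3 × 20 × 0.964 = 5.8 |
| 70 | 15 | −0.333 | 0.598 | 0.3 × 15 × 0.598 = 2.7 |
| 70 | 20 | −0.250 | 0.646 | 0.3 × 20 × 0.646 = 3.9 |

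**Sensitivity.** At m = 60 and s = 20, the fall is 9.6 mm for r = 0.5 and 3.9 mm for r = 0.8. Over means of 50, 60, 70 and 75, SDs of 15, 20 and 25, and correlations of 0.5, 0.6, 0.7 and 0.8, it runs from 1.3 mm (75, 15, 0.8) to 15.2 mm (50, 25, 0.5). That last combination is the only one of the 48 to reach 14 mm. Simulation on a scale clipped to 0-100 agreed with the formula within about 0.1 mm in the cases run.

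**Separate Day 0 baseline that plays no part in eligibility.**
- If the correlation does not decay with time, the expected fall from Day 0 to follow-up is 0.0 mm.
- If it does decay, some bias remains. Take m = 60 and s = 20, with correlations of 0.8 (screening to Day 0), 0.6 (screening to follow-up) and 0.7 (Day 0 to follow-up). The fall is 0.4 × 20 × 0.964 = 7.7 mm from the screening mark and (0.8 − 0.6) × 20 × 0.964 = 3.9 mm from the Day 0 mark (3.8 mm by simulation), so it is about halved.

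**Randomised contrast.** Both arms pass the same cut and regress equally in expectation. With 1:1 allocation at m = 60, s = 20 and r = 0.6, the simulated between-arm difference was −0.006 mm, which is zero within simulation error.

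**The case against.** The strongest reply is that the documents do not fix a biased baseline. Both schedules mark a Visit 2 pain assessment, 3.6.1 permits one, and the SAP allows a Day 0 baseline. That stands. A reader might infer that most subjects give only one pre-operative VAS, but no section states that share. What can be said is that the procedural sections guarantee no second pre-block mark and that the sections conflict.

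Three other stronger readings also fail:
- That a 15-subject pilot would often show a falsely significant benefit. The SAP plans descriptive statistics and no pilot test, and study success in Protocol 5.10 rests on superiority over neurectomy. The harm is to how the pilot mean is read.
- That every within-arm change is inflated. Entry selects on the VAS alone. PROMIS and FHSQ are affected only through their correlation with it, which the documents do not give.
- That the comparison with historical controls named in the synopsis is biased by a known amount. That depends on how those subjects were selected, which is not stated.

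The Daily Pain Diary, issued at screening and reviewed on Day 0, does give pre-operative ratings that play no part in eligibility. It is a partial cross-check, but it uses a 10-point scale and is not the baseline of the VAS endpoint.

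**Conclusion.** The concern holds as a conditional one. If the screening mark is the baseline, which 3.6.1, 3.9.1 and 3.9.2 make the default, then the pilot VAS change, each arm's own VAS change and the 5.5.1 interval on the Nerve Cap arm include regression to the mean. A plausible size is about 3-6 mm (assumed mean 60-70 mm, SD 15-20 mm, correlation 0.7), and it stays below 14 mm in nearly all of the wider assumed range. The mechanism is certain once that mark is used. The size is not known from the documents.

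A reader might go further and infer that the 12-month comparison overstates the device's benefit. It does not on this account: randomisation makes the fall equal in the two arms in expectation.

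**What to change.** **Protocol.** In 3.9.2 item 5, require a pre-block VAS on Day 0 from every subject, whether or not one was taken at screening. Bring 3.6.1, Appendix B footnote 3 and the matching SAP schedule footnote into line.

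**SAP section 6.** Define baseline VAS as the Day 0 pre-block mark. Bar any post-block value from the fallback to the latest pre-repair value. Use the screening VAS for eligibility only, and do not re-apply the 65 mm cut to the Day 0 mark, since that would bring the selection back.

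**Special cases.** For subjects screened and operated on the same day, keep the single mark and show the VAS change with and without them. For pilot subjects already enrolled with only a screening mark, report the change with a plain statement that it includes regression to the mean. A numerical correction would need the unselected VAS distribution and an untreated repeat correlation, and the documents give no source for either.

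**Cost.** One 100 mm line per subject at a scheduled visit, plus short text changes in both documents. The reported baseline and mean change may be a few mm smaller. Same-day subjects gain nothing, because their one mark is still the qualifying mark. If the correlation falls with time, the bias is reduced rather than removed.
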